**2. Background:**

Amniotomy, i.e. artificial rupture of amniotic membranes, has become a common method used in management of both induction and augmentation of labor. It has been shown to shorten the duration of labor. Risks associated with amniotomy include ascending infection, fetal heart rate decelerations, umbilical cord prolapse, and rupture of vasa previa. While there are risks associated with amniotomy, there are also risks associated with prolonged labor, including an association with cesarean delivery and decreased fetal cord pH.

Timing of amniotomy in the management of induction of labor has not been widely studied. The limited studies have mixed results, but a recent meta-analysis suggests that early amniotomy shortens the length

of labor and has no effect on rates of cesarean section. However, these studies use a variety of methods for cervical ripening prior to amniotomy, which may affect the outcome as well. Additionally, the studies differed in whether they compared early amniotomy to delayed amniotomy or spontaneous rupture of membranes. Levy et al. showed longer labors with increased cesarean section rates in those receiving early amniotomy after cervical ripening with a Foley balloon. These results may be in part due to the fact that oxytocin infusion was not initiated in these subjects until the labor progress was deemed to be inadequate.

With the limited amount of published research, and conflicting results, more data is needed to be able to determine the ideal time for amniotomy during the management of the induction of labor, specifically when using a Foley balloon for cervical ripening.

The primary objectives of this study are to evaluate time to reach active phase of labor (defined as 6 cm or more of cervical dilation). The secondary objectives of this study are to evaluate in these subjects 1) cesarean section rates and indications, 2) occurrence of maternal complications including isolated maternal fever, chorioamnionitis, postpartum hemorrhage, endometritis, wound infection, and 3) occurrence of neonatal complications including umbilical cord prolapse, Apgar score <7 at 1 and 5 minutes, cord pH <7.0, NICU admission, neonatal infection. We will also be looking at time to vaginal delivery and vaginal deliveries within 24, 36 and 48 hours.

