## Study Summary Flow Diagram

#### 4.9. Primary Outcomes

- Time interval from Foley balloon placement to reaching the active phase of labor (6 cm cervical dilation)

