#### 4.10 Secondary Outcomes

- Induction to delivery time in minutes
- Time interval from completion of cervical ripening to delivery in minutes
- Vaginal delivery within 24, 36 and 48 hours of induction
- Cesarean section rates and indications
- Operative delivery rates
- Total length of hospital stay
- Maternal outcomes
  - Isolated maternal fever
  - Chorioamnionitis (also known as “IAI,” or “triple I”):
    - A **presumptive diagnosis** of IAI (suspected triple I) can be made in women with:
      - **Fever** –  $\geq 39.0^{\circ}\text{C}$  [ $102.2^{\circ}\text{F}$ ] **or**  $38.0^{\circ}\text{C}$  [ $100.4^{\circ}\text{F}$ ] to  $38.9^{\circ}\text{C}$  [ $102.02^{\circ}\text{F}$ ] on two occasions 30 minutes apart, without another clear source **PLUS** one or more of the following [1]:
        - Baseline fetal heart rate  $>160$  beats/min for  $\geq 10$  minutes, excluding accelerations, decelerations, and periods of marked variability
        - Maternal white cell count  $>15,000/\text{mm}^3$  in the absence of corticosteroids and ideally showing a left shift (bandemia)
        - Purulent-appearing fluid coming from the cervical os visualized by speculum examination
      - A **confirmed diagnosis** of IAI can be made in women with:
        - **All of the above** **PLUS** one or more of the following objective laboratory findings:
          - Positive Gram stain of amniotic fluid
          - Low glucose level in amniotic fluid
          - Positive amniotic fluid culture
          - High white cell (WBC) count in amniotic fluid in the absence of a bloody tap
          - Histopathologic evidence of infection or inflammation or both in the placenta, fetal membranes, or the umbilical cord vessels (funisitis)
        - Endometritis - must meet the following criteria:
          - Infection occurs within 30 days after the operative procedure AND
          - Infection presumed to involve the uterus AND
          - Subject has at least one of the following:

- Purulent drainage from a drain that is placed through a stab wound into the abdomen or pelvis
- Organisms isolated from an aseptically-obtained culture of fluid or tissue in the organ / space
- Postpartum hemorrhage
  - EBL >1000 cc
- Wound infection
- Umbilical cord prolapse
- Neonatal outcomes
  - Apgar score <7 at 1 and 5 minutes
  - Cord arterial pH <7.0
  - NICU admission

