## 13. Statistical Approach

Analysis will be performed by intent to treat. Univariable and multivariable analysis will be used to describe the population in the study and to identify potential confounding variable. For this analysis normality will be tested using Shapiro-Wilk method. Demographics and descriptive statistics such as t test, Pearson's chi square, and Mann-Whitney tests will be used as indicated. Data will be either shown as median +/- Range or mean +/- SDEV. Statistical analyses of primary and secondary outcomes between two groups will be performed by multivariate logistic regression analysis accounting for confounding variables if indicated.

Based on our prior results (DILAFOL Trial), women who received Foley balloon and delayed amniotomy reached active phase of labor in 1111 mins with a standard deviation of 525 mins. Using difference rate of 25%, power of 90% and 2-sided alpha of 0.05, we estimate that we will need 150 with complete ascertainment. This difference of 278 or ~4hours was decided after consulting clinical experts in the field of obstetrics, supporting clinical reasoning that a difference between both methods is clinically significant. Detailed from stata 16 : Estimated sample sizes for a two-sample means test (z test) ;Study parameters: alpha = 0.0500; power = 0.9000; delta = -278.0000; mean1 = 1111.0000; mean2 = 833.0000 sd = 525.0000 Estimated sample sizes: N = 150

N per group = 75. Assuming a 13% loss to follow, we propose to enroll a total of 174 subjects. Analyses will be performed by intent to treat. We will be using STATA 16 (Dallas, TX) for statistical computations

This trial will be registered with Clinical Trials Register (Clinicaltrials.gov), before recruitment is initiated and after IRB approval.

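### Section 13 assigns the primary outcome, a time in minutes, to logistic regression, which cannot estimate the 278-minute difference in means on which N = 150 rests

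*Combined protocol and SAP*

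**What the plan says.** Section 4.9 lists one primary outcome: "Time interval from Foley balloon placement to reaching the active phase of labor (6 cm cervical dilation"). Section 2 agrees: "The primary objectives of this study are to evaluate time to reach active phase of labor". Neither section defines a yes/no version or a cut-point.

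Section 13 contains three statements that matter here:

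- **Sizing.** The software output is headed "Estimated sample sizes for a two-sample means test (z test"), with means of 1111 and 833 minutes, SD 525, two-sided alpha 0.05 and power 90%. From this, "we estimate that we will need 150 with complete ascertainment". Enrolment is then raised: "Assuming a 13% loss to follow, we propose to enroll a total of 174 subjects".
- **Tests suited to continuous data.** A Shapiro-Wilk check is planned, and the t test and Mann-Whitney test are named, but in a sentence that opens "Demographics and descriptive statistics such as t test".
- **Analysis of outcomes.** The only sentence that assigns a method to the primary outcome is "Statistical analyses of primary and secondary outcomes between two groups will be performed by multivariate logistic regression analysis accounting for confounding variables if indicated".

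Several secondary outcomes are also durations. Section 4.10 has "Induction to delivery time in minutes", the interval from the end of ripening to delivery, and length of hospital stay. Section 2 adds time to vaginal delivery.

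**The concern.** Logistic regression models the probability of a category and returns an odds ratio. It does not accept a time in minutes as its outcome, and it neither estimates nor tests a difference in mean minutes. The method named for the primary outcome is therefore not the method behind the 90% power, and it cannot deliver the 278-minute contrast that section 13 calls clinically significant.

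Two things are at stake. An analyst who follows the sentence must turn the time into a binary outcome at a cut-point chosen later, and loses power by doing so. An analyst who departs from it must choose among a t test, a Mann-Whitney test and some adjusted model with covariates that are not named. In an unblinded trial, that choice should be fixed before the outcome data are examined.

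**Working it through.** **Inputs from section 13.** Means 1111 and 833 minutes, difference 278, common SD 525, two-sided alpha 0.05, power 0.90, 75 per arm, 174 enrolled, 13% loss. Section 4.2 gives 1:1 allocation.

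**1. Reproduce the plan's figure.** n per arm = 2 × (z₀.₉₇₅ + z₀.₉₀)² × SD² / difference² = 2 × (1.960 + 1.2816)² × 525² / 278² = 74.95. This rounds up to 75 per arm, 150 in total, as stated. For enrolment, 174 × 0.87 = 151.4, which covers 150.

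**2. Power of the means comparison at 75 per arm.** The standard error is 525 × √(2/75) = 85.7 minutes, and 278 / 85.7 = 3.243. The z-test power is Φ(3.243 − 1.960) = 0.900, and the t-test power (noncentral t, 148 df) is 0.896. The expected 95% CI half-width is t(0.975, 148) × 85.7 = 169 minutes.

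**3. Power if the logistic sentence is applied literally.** Assumptions, none from the documents: normal times with the stated means and SD, an unadjusted two-proportion approximation, and the cut-points below. For cut-point c, the proportion at 6 cm by time c is Φ((c − 1111)/525) under delayed amniotomy and Φ((c − 833)/525) under early amniotomy. With d the difference in proportions and p̄ their mean:

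power = Φ((d − 1.960 × se₀) / se₁), where se₀ = √(2p̄(1 − p̄)/75) and se₁ = √((p₁(1 − p₁) + p₂(1 − p₂))/75).

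Example at 972 minutes: p₁ = 0.396, p₂ = 0.604, d = 0.209, se₀ = 0.0816, se₁ = 0.0798. Power = Φ((0.2088 − 0.1600)/0.0798) = 0.73.

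| Cut-point (min) | Delayed | Early | Power at 75 per arm | Evaluable total for 90% |
|---|---|---|---|---|
| 720 | 22.8% | 41.5% | 0.69 | 260 |
| 833 | 29.8% | 50.0% | 0.72 | 244 |
| 972 | 39.6% | 60.4% | 0.73 | 238 |
| 1111 | 50.0% | 70.2% | 0.72 | 244 |
| 1440 | 73.5% | 87.6% | 0.59 | 326 |

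**4. Are 75 observed times per arm enough after the correction?** Not by themselves. Section 4.2 analyses every randomized woman, yet a woman delivered by cesarean before 6 cm has no primary value. As an illustration, assume normal times as above and that women not at 6 cm by a limit L never get a value. The observed times are then normal, truncated above at L. With a = (L − mean)/525 and λ = φ(a)/Φ(a), the observed mean is mean − 525λ and the variance is 525² × (1 − aλ − λ²).

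- L = 1800: 9.5% (delayed) and 3.3% (early) have no value. Observed means are 1013 and 793, SDs 446 and 485. The difference is 220 minutes, its standard error at 75 observed per arm is √((446² + 485²)/75) = 76.1, and z-test power is Φ(220/76.1 − 1.960) = 0.82.
- L = 1440: 26.5% and 12.4% have no value. Observed means are 877 and 710, SDs 379 and 432. The difference is 166 minutes, its standard error is 66.3, and power is 0.71.

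The limits are assumptions. The documents give no rate of women without a 6 cm time, and do not say whether 1111 and 525 already exclude such women.

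**The case against.** The best defence is that section 13 plainly has continuous data in mind. It sizes the trial on means in minutes, plans a normality check, names the t test and Mann-Whitney test for use as indicated, and reports means or medians. The regression sentence ends with a condition about confounders, so it could be an optional adjusted step aimed mainly at the many binary outcomes in section 4.10. On that reading the primary test is a t test or a Mann-Whitney test, and the fault is loose drafting.

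Part of this stands. It would be too strong to infer that the plan contains no time-scale method, or that the investigators mean to dichotomise; the documents do not show either. But the two-stage reading is nowhere stated. The time-scale tests are attached to demographics and description, and the regression sentence names the primary outcome. Even if the reading is granted, two faults remain: logistic regression is the wrong adjusted model for minutes, and the choice of primary test is still open.

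A second objection is that the t test is one remedy among several. That is fair: a linear or time-to-event model would also cure the mismatch. The difference in means is preferred here only because it is the comparison for which N = 150 was computed.

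**Conclusion.** The analysis sentence in section 13 is wrong as written for the primary outcome and for the secondary outcomes that are durations. It should be corrected before analysis, because it concerns the confirmatory test of the only primary outcome and separates that test from the sample size.

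The cost of literal application, a fall in power from 0.90 to about 0.59–0.73, depends on normal times and assumed cut-points. It is a consequence of following the sentence, not a prediction of what the investigators will do.

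Two further inferences should be resisted. One is that N = 150 is wrong or that recruitment must rise to 238–326: the figure reproduces exactly for the means comparison, and the larger totals apply only to a dichotomised outcome that nobody has specified. The other is that 75 observed times per arm guarantee 90% power: that also requires that women without a 6 cm time do not distort the difference between arms, on which the documents give no information.

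**What to change.** Revise section 13 as follows:

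- Confine logistic regression to the binary outcomes, such as cesarean, vaginal delivery within 24, 36 and 48 hours, and chorioamnionitis.
- Name one time-scale primary analysis. The one that matches N = 150 is the difference in mean minutes with a 95% CI, by two-sample t test or, if adjustment is wanted, by linear regression with covariates listed in advance.
- Analyse induction to delivery, ripening to delivery, time to vaginal delivery and length of stay on the time scale as well.
- Report by arm the number of randomized women without a 6 cm time, and add one sensitivity analysis that keeps them all, such as a worst-rank test or a time-to-event analysis.
- State that the 90% power applies to the means comparison, given about 75 women per arm with a 6 cm time and no distortion from those without one. N = 150 has not been shown for a time-to-event primary analysis, since no event count or hazard ratio is given.

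The cost is a few sentences written before the data are analysed, with no extra patients.

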#### **4.2. Randomization and Masking**

A confidential computer-generated simple randomization scheme (using STATA 16, Dallas, TX) has been prepared. A randomization log with group assignment, subject name, and medical record number will be used to track the randomization process.

Subjects will be randomized in a ratio of 1:1 for delayed or early amniotomy.

Due to the nature of the intervention, blinding of subjects or providers will not be possible.

The subject will be included in the analysis by intent-to-treat once the randomization assignment has been made.

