#### **4.4. Baseline Procedures**

Routine intrapartum care will be provided by the subject's managing obstetric team.

Trained and experienced research staff will be responsible for all research data abstraction.

The PI and collaborators will review and validate the diagnosis for all subjects identified to have the primary outcomes.

Maternal and neonatal outcomes will be assessed following delivery.

Subjects will be encouraged to call the principal investigator with any concerns.

Data collection forms will be used during these processes and charts will be reviewed up to 30 days postpartum. We will collect demographic data, as well as data related to the subject's intrapartum course, delivery, and immediate postpartum period while inpatient. Data on newborn status, including those admitted to the NICU, will be obtained from the infants' charts.

Subjects' participation will end after being discharged home from the hospital.

[figure not shown]

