#### **4.6. Withdrawals**

Subjects who withdraw from the study after randomization will be excluded from further follow-up. Outcomes ascertained up until the time of withdrawal will be reported in intent-to-treat fashion.

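### The primary outcome is a time to 6 cm, but the plan assigns it logistic regression and gives no rule for women delivered by cesarean before 6 cm

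*Combined protocol and SAP*

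**What the plan says.** - **Outcome.** Section 4.9 lists one primary outcome: "Time interval from Foley balloon placement to reaching the active phase of labor (6 cm cervical dilation".
- **Method.** Section 13 says: "Statistical analyses of primary and secondary outcomes between two groups will be performed by multivariate logistic regression analysis accounting for confounding variables if indicated". It names the t test, chi-square and Mann-Whitney in the sentence on demographics and descriptive statistics. It names no survival, censoring or competing-event method, and no cut-point that would make the time binary.
- **Sizing.** Section 13 uses a two-sample z test of means: 1111 versus 833 minutes, SD 525, 90% power, two-sided alpha 0.05. This gives 150 women with complete ascertainment, raised to 174 for a 13% loss to follow-up.
- **Who is analysed.** Section 4.2: "The subject will be included in the analysis by intent-to-treat once the randomization assignment has been made". Section 4.3 keeps women whose amniotomy falls outside the time limits. Section 4.6 deals with withdrawals: "Subjects who withdraw from the study after randomization will be excluded from further follow-up".
- **Cesarean.** It appears among the secondary outcomes in section 4.10: "Cesarean section rates and indications". No expected rate is given, before 6 cm or overall.

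**The concern.** There are two linked gaps. The named method models a binary outcome, while the outcome is a time and the sample size belongs to a comparison of means. And a woman delivered by cesarean before 6 cm never has the primary outcome. Intention to treat fixes the arm she is counted in but supplies no value for a time that was never reached.

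If such women are simply left out, the comparison is among women selected after randomization. Where the omitted labors are the slow ones, the arm with more of them looks faster. An arm could then appear better because more of its women were delivered by cesarean before 6 cm.

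Different rules can also err in opposite directions on the same data, as shown below. That is a reason to fix the rule in advance in a trial where "blinding of subjects or providers will not be possible".

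**Working it through.** **1. The plan's own figure.** Inputs from section 13: difference 278, SD 525, z-values 1.960 and 1.2816.

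n per arm = 2 × [(1.960 + 1.2816) × 525 / 278]² = 74.95, so 75 per arm and 150 in total. Then 75 / 0.87 = 86.2, so 87 per arm and 174 in total. The arithmetic reproduces. It describes a means test on 150 observed times, not a logistic regression.

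**2. Is there a rule anywhere?** Section 4.2 includes every randomized woman. Section 4.3 covers mistimed amniotomy. Section 4.6 covers withdrawals. Section 13 repeats intention to treat. None gives a value, rank or censoring status to a woman delivered before 6 cm. The t test needs an observed time. Mann-Whitney could include her only if she were assigned a rank, and no such rule is given.

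**3. Could the 13% allowance absorb these women?** 174 − 150 = 24 women. If 10% or 15% had a cesarean before 6 cm (assumed), that would be 17.4 or 26.1 women before any other loss. If ordinary loss already uses the allowance, leaving 75 per arm, dropping a further 10% or 15% at random lowers the means-test power from 90.0% to 86.8% or 84.8%.

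**4. Size of the possible bias (simulation; all cesarean rates are assumptions).** Gamma times with mean 1111 and SD 525 in both arms, so no effect on time; 87 per arm. Cesarean before 6 cm depends on standardized time through a logistic slope of 0 (unrelated), 1 or 2, or falls on exactly the slowest labors. Shift is early minus delayed among observed times. Error is total two-sided rejection, with 5% nominal.

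| Early vs delayed | Dependence | Shift, min | Observed-times t | Cause-specific log-rank | Rank test, these women last |
|---|---|---|---|---|---|
| 15% vs 10% | slope 0 | 0 | 5.2% | 6.2% | 8.6% |
| | slope 1 | −23.1 | 5.9% | 5.3% | 6.2% |
| | slope 2 | −32.9 | 7.9% | 5.2% | 5.6% |
| | slowest | −43.2 | 11.1% | 5.4% | 5.2% |
| 18% vs 8% | slope 0 | 0 | 4.9% | 8.0% | 20.7% |
| | slope 1 | −46.1 | 8.9% | 6.2% | 11.2% |
| | slope 2 | −65.5 | 15.4% | 5.9% | 7.6% |
| | slowest | −85.9 | 28.7% | 5.6% | 5.6% |

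The largest shift is 85.9 / 278 = 31% of the planned difference. Equal rates give no shift and about 5% error for every test. Reversed rates mirror the table. Log-rank figures assume cesarean at a uniform 60–100% of the time at which 6 cm would have been reached.

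On direction: at 18% versus 8% and slope 1, the observed-times t test favors early amniotomy in 8.4% of trials, and the rank test favors delayed in 10.8%, against 2.5% expected on each side.

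**5. Power of the log-rank test.** 1111 versus 833 minutes, equal cesarean rates, 87 or 76 women per arm (87 × 0.87 = 75.7). Each cell gives power at 10% / 15% cesarean, slope 1.

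| | 87 per arm | 76 per arm |
|---|---|---|
| SD 525 in both arms | 81.4% / 79.4% | 76.6% / 74.6% |
| Early-arm SD 394 (times 25% shorter) | 95.8% / 94.6% | 93.2% / 91.4% |

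At slope 0 with SD 525, 15% and 76 per arm, power is about 72%. Over slopes 0 to 1 the ranges are therefore about 72–81% and, allowing for simulation error, about 91–97%. The early-arm SD matters because equal SDs around a shorter mean give the early arm a relatively longer tail, which costs the log-rank test power.

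**The case against.** - **The logistic sentence may be loose drafting.** It covers primary and secondary outcomes together, several secondary outcomes are binary, and the qualifier at its end may mean that regression is only for adjustment. The sizing points to a comparison of means. This is a fair reading, but it does not close the gap: logistic regression would not adjust a time either, and neither the t test nor Mann-Whitney as named deals with women who have no 6 cm time.
- **The harm is conditional.** Bias needs unequal rates and cesareans concentrated in slow labors. Section 1 reports one trial with more cesareans after early amniotomy and a meta-analysis with no change. Section 2 attributes the adverse trial partly to oxytocin being started only once progress was judged inadequate. At 15% versus 10% and slope 1 the error is 5.9%, barely above nominal. This stands, and it limits what can be claimed about size.
- **No alternative is free.** Ranking these women last can distort more than dropping them: 20.7% against 4.9% error at 18% versus 8%, slope 0. Log-rank is also moved by a cesarean difference, up to 8.0%. With equal rates and SD 525 the observed-times t test has more power than log-rank. This stands. It argues for choosing openly, and against treating the rank test as required.
- **A reader might infer that the plan intends to drop these women.** It does not say so. Section 4.4 says "The PI and collaborators will review and validate the diagnosis for all subjects identified to have the primary outcomes", but that concerns data checking, not the analysis set. Omission is only the likely default, and it would depart from section 4.2.

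**Conclusion.** The point holds on the text, without any assumed rate. The only method stated for the sole primary outcome does not fit a time, and no rule covers women delivered before 6 cm.

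The size of the harm cannot be read from the documents. On the assumed settings it runs from nothing to 43 minutes and 11% error (15% versus 10%), or to 86 minutes and 29% error (18% versus 8%). The upper ends need exactly the slowest labors to end in cesarean.

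Two stronger readings are not supported. A reader might infer that the trial will be biased toward early amniotomy, but the direction depends on which arm has more such cesareans, and the evidence cited in the plan is mixed. A reader might also infer that 150 is wrong; it is right for the means test it describes, and only its link to the named analysis is missing.

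Priority lies between should-fix and must-fix: it concerns the sole primary analysis, but the damage is unquantified.

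**What to change.** In section 13:

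1. Limit logistic regression to the binary secondary outcomes.
2. For the primary outcome, prespecify one time-to-event comparison of all randomized women from Foley placement to 6 cm: log-rank or cause-specific Cox, with delivery before 6 cm ending follow-up as a competing event. Cox can carry prespecified covariates if adjustment is wanted.
3. Show the cumulative incidence of 6 cm by arm. Report minutes among women who reached 6 cm as descriptive.
4. If a rank test placing these women last is added, make it a sensitivity analysis and label it a composite that a cesarean difference alone can move.
5. State whether the 13% allowance covers women without a 6 cm time, and that the 90% power belongs to a means test on 150 observed times.
6. Restate power for the chosen test with its assumptions. For log-rank with 10–15% such cesareans in both arms and 76–87 women per arm, it is about 72–81% if both SDs are 525 and about 91–97% if the early-arm SD is 394, with cesarean unrelated to labor speed or moderately related to it (slope 0 to 1).

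Cost: SAP wording, a headline result that is no longer a mean difference in minutes, and a power figure that may be below 90%. No new data are needed, because section 4.10 already requires cesarean status and "Induction to delivery time in minutes".

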### **3. Concise Summary of Project:**

- The target population for our study is both nulliparous and parous women who present for induction of labor. If there is a decision by the obstetric team to place a transcervical Foley balloon for cervical ripening, the obstetric team will notify the research team so that the patient may be screened for the study. If the subject consents to participation, written informed consent will be obtained by person-to-person contact. The PI or a collaborator will be responsible for the informed consent. After informed consent is obtained, the transcervical Foley balloon will be placed. The method of placement will be left to the discretion of the provider. After placement of the Foley balloon, the subject will be randomized to the study group (early amniotomy) or the control group (delayed amniotomy).

The control group will undergo amniotomy at least four hours after expulsion of the Foley balloon.

The study group will undergo amniotomy as soon as possible after Foley balloon expulsion or within two hours of expulsion.

At any point, if the treating provider determines amniotomy is unsafe, amniotomy may be delayed and performed as soon as the provider deems safe.

This will be an unblinded randomized clinical trial.

No significant adverse effects are expected with the use of amniotomy. The most significant risks associated with amniotomy are fetal heart rate decelerations, ascending infection, umbilical cord prolapse (<1%), rupture of vasa previa (<1%). The subject will undergo inpatient induction of labor, so any adverse reaction would be promptly detected and addressed.

- The number of subjects studied will be 174 subjects at UTMB. The subjects will be withdrawn from the study if she wishes to discontinue participation. If any of the exclusion criteria listed above are met, or there is a change in condition that leads to inclusion

criteria no longer being met, data collection will be terminated and the subject will be withdrawn from the study.

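### Section 13 assigns all secondary outcomes to logistic regression, but at the protocol's own cord prolapse risk of under 1% at least one arm will usually have no events, leaving no usable odds ratio

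*Combined protocol and SAP*

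**What the plan says.** Section 13 (Statistical Approach) is the whole analysis plan. Its rule for outcomes is one sentence, under which analyses of primary and "secondary outcomes between two groups will be performed by multivariate logistic regression analysis accounting for confounding variables if indicated". Just before it, after text on describing the population and looking for confounders, comes a list of simple tests: "Demographics and descriptive statistics such as t test, Pearson's chi square, and Mann-Whitney tests will be used as indicated". The section names no exact test, no penalized or exact logistic model, and no rule for outcomes with few events.

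Cord prolapse falls under the outcome rule. Section 2 includes it in the secondary objectives: "occurrence of neonatal complications including umbilical cord prolapse, Apgar score <7 at 1 and 5 minutes, cord pH <7.0". Section 4.10 lists "Umbilical cord prolapse" again among the secondary outcomes. Section 3 gives its risk with amniotomy as below 1%. Section 9.1 names it among the complications whose rates might differ when amniotomy is done earlier.

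Section 13 plans 75 women per group with complete data and 174 enrolled. Section 4.2 specifies 1:1 allocation by simple randomization.

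**The concern.** A logistic model estimates the treatment odds ratio by comparing the odds of the event in the two arms. If one arm has no events, the likelihood has no finite maximum for that coefficient. The odds ratio is then 0 or infinite, and whatever coefficient and standard error the software prints depend on where the iteration stopped. If neither arm has an event, there is nothing to model. Adding covariates does not help, and neither does removing them.

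At these arm sizes a risk below 1% means less than one expected prolapse per arm, so an empty arm is the ordinary case. Following the plan literally would then mean reporting a meaningless number, reporting nothing, or choosing another method after the data are seen in an unblinded trial. The outcome is a safety question that the protocol itself raises. A bare statement that no significant difference was found could be taken as reassurance when the data exclude very little.

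This is separate from the question of whether a logistic model suits a time-to-event outcome. Resolving that would leave this gap open.

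**Working it through.** **Inputs from the document.** Section 13: means 1111 and 833 minutes, difference 278, SD 525, two-sided alpha 0.05, power 90%, 75 per group, 13% loss, 174 enrolled. Section 3: prolapse risk below 1%. Section 4.2: 1:1 simple randomization.

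**Assumptions.** The document gives only a ceiling for prolapse, so I use 1% (the ceiling), 0.5% and 0.1%, with the same rate in both arms unless stated.

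**1. Arm sizes.** n per arm = 2(1.960 + 1.282)² × 525² / 278² = 74.9, rounded up to 75, or 150 in total. Loss: 75 / 0.87 = 86.2, rounded up to 87 per arm, or 174. The plan's figures reproduce, so the relevant range is 75 to 87 per arm.

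**2. Expected events.** At 1%: 75 × 0.01 = 0.75 and 87 × 0.01 = 0.87 per arm.

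**3. Chance of an empty arm.** Let q = (1 − p)^n be the chance of no events in one arm. Then P(at least one arm empty) = 1 − (1 − q)² and P(both empty) = q².

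Worked case, p = 1%, n = 87: q = 0.99^87 = 0.417; 1 − (0.583)² = 0.660; q² = 0.174.

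| Rate in both arms | n per arm | q | At least one arm empty | Both arms empty |
|---|---|---|---|---|
| 1% (ceiling) | 87 | 0.417 | 66.0% | 17.4% |
| 1% (ceiling) | 75 | 0.471 | 72.0% | 22.2% |
| 0.5% (assumed) | 87 | 0.647 | 87.5% | 41.8% |
| 0.5% (assumed) | 75 | 0.687 | 90.2% | 47.2% |
| 0.1% (assumed) | 87 | 0.917 | 99.3% | 84.0% |
| 0.1% (assumed) | 75 | 0.928 | 99.5% | 86.1% |

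**4. Sensitivity.**
- Simple randomization lets the arm sizes vary. Averaging over this raises the 1% figures by about 0.2 percentage points.
- The chance of an empty arm falls to 50% when p = 1 − (1 − √0.5)^(1/n). This is 1.4% at 87 per arm and 1.6% at 75, both above the protocol's ceiling.
- Unequal rates use 1 − (1 − q₁)(1 − q₂). With 1% in one arm and 0.5% in the other, the chance is 79% (87 per arm) to 83% (75 per arm). With 2% and 1%, the first above the ceiling, it is still 52% to 59%.

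**5. What zero events would exclude.** The exact two-sided 95% upper limit for 0 of n is 1 − 0.025^(1/n): 4.2% for n = 87 and 4.8% for n = 75. Either is more than four times the 1% ceiling.

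**The case against.** **The list of tests is open, so Fisher's test is not ruled out.** The list is illustrative and its tests are to be used as appropriate. This is partly right: nothing forbids an exact test. But the list concerns demographics and descriptive statistics, and the sentence on outcomes names logistic regression. The qualifier at the end of that sentence most naturally attaches to confounder adjustment, and an unadjusted logistic model fails on an empty arm in the same way.

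**The shortage is of events, not of method.** This largely stands. With under one expected event per arm, no analysis will be informative about prolapse. Exactly one arm is empty in about 49% to 50% of trials at 1%, and where both are empty no method yields an odds ratio. The change improves what is reported; it adds no information. That is still worth having, because counts and an exact interval show the reader how little is known.

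**A reader might infer that the listed methods would contradict each other on the same table.** The document does not support this. Section 13 does not clearly assign chi-square to outcome testing, and it does not say that the logistic comparison would use a Wald test. For an illustrative 4 of 87 against 0 of 87, the likelihood-ratio test from the unadjusted logistic model gives p = 0.018 and Pearson's test gives p = 0.043, both below 0.05. Such a table is also improbable: 0.8%, counting both directions, at 1% in each arm. A likelihood-ratio p-value can thus be obtained with one empty arm; what is lost is a finite estimate.

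**A reader might also extend the point to cord pH below 7.0, endometritis or wound infection.** The document gives no rate for any of them, so their rarity cannot be asserted. The fix should be triggered by the data, with only prolapse named in advance.

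**Conclusion.** The point holds for cord prolapse. Across the range the protocol allows, the method that Section 13 names will more often than not meet an arm with no events: 66% to 72% at the 1% ceiling, and more at any lower rate. The odds ratio is then 0, infinite or not estimable.

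This rests on three things: reading the outcome sentence in Section 13 as applying to every secondary outcome, as it says; applying Section 3's general risk figure for amniotomy to both arms, with 0.5% and 0.1% as assumed alternatives; and 75 to 87 women per arm. It does not depend on which covariates are chosen.

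The weight is moderate. One rare secondary safety outcome is affected on the documented figures. It is nevertheless more than a missing detail, because the stated method usually fails for an outcome that the protocol lists and flags as a possible harm. Section 13 makes no claim that a null result would show safety, so misreading is a risk in reporting and not an error in the plan.

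**What to change.** Add to Section 13, before outcome data are examined: cord prolapse, and any other binary outcome with no events in one arm or an expected cell count below 5, will be reported as counts by arm and compared without covariates by Fisher's exact test, with an exact 95% confidence interval for the risk difference. A non-significant result for these outcomes will be reported as the range of differences not excluded. With equal arms, an expected count below 5 means fewer than 10 events in total.

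Keep logistic regression for the commoner binary outcomes, such as cesarean section and vaginal delivery within 24, 36 and 48 hours.

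The cost is two or three sentences and routine software, with no added participants, data or change to care. The downsides are that Fisher's test is conservative and that these comparisons are unadjusted.
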